9.3.4 Tertiary/exploratory endpoints

9.3.5 Other/safety analysis

All safety analyses will be performed on the safety population.

Safety summaries will be descriptive, ie, no statistical significance tests will be performed on safety data. The summary of safety results will be presented by treatment group.

Safety analyses will be based on the reported AEs and other safety information, such as clinical laboratory data, vital signs, and ECG.

9.3.5.1 Adverse events

General common rules for adverse events

The AEs during the DB period will be analyzed in the following 3 categories (see [Section 9.3.1](#)):

- Pre-treatment AEs: AEs that developed, worsened, or became serious during the pre-treatment period.
- TEAEs: AEs that developed, worsened, or became serious during the DB on-treatment period
- Post-treatment AEs: AEs that developed, worsened, or became serious during the post-treatment period, if applicable.

Similarly, the deaths will be analyzed in the pre-treatment, DB on-treatment, and post-treatment periods.

Analysis of all adverse events

Adverse event incidence tables will be provided by treatment group for all types of TEAEs: all TEAEs, all TE AESIs (defined with a Preferred Term or a prespecified grouping), all TE SAEs, and all TEAEs leading to permanent treatment discontinuation.

The AE summaries will be generated with number (%) of participants experiencing at least one event.

Deaths will also be analyzed.

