4 STUDY DESIGN

4.1 OVERALL DESIGN

[figure not shown]
EFC17262 is a multicenter, randomized, DB, placebo-controlled, Phase 3 study to evaluate the efficacy and safety of tolebrutinib 60 mg daily compared with placebo in participants aged 18 to 85 years with moderate-to-severe gMG, who are receiving the SoC. The DB period will be followed by an OLE period to evaluate the safety and efficacy of tolebrutinib.

The DB period will include a screening period (up to 28 days) and a treatment period of 26 weeks. After screening, eligible participants will be randomly assigned (1:1 ratio) to receive 60 mg of a daily dose of oral tolebrutinib or matching placebo. Randomization will be stratified by MGFA class (II, IIIa/IVa, or IIIb/IVb) and region (US, non-US). The primary endpoint will be change from baseline in the MG-ADL score at Week 26.

Participants will receive the IMP as an add-on therapy to their SoC, ie, their gMG treatment(s) prior to screening maintained at stable doses throughout the 26-week duration of the DB period. These treatments are required to be at stable doses for a predefined duration prior to the entry in the study; see details in the inclusion criteria ([Section 5.1](#)). The SoC may consist of an AChEI (eg, pyridostigmine), an OCS up to the maximal dose of 20 mg daily, and/or a single IST, such as azathioprine, mycophenolate mofetil, tacrolimus, or methotrexate.

The use of rescue therapy for gMG worsening will be allowed at the discretion of the Investigator if there is at least a 2-point increase of individual non-ocular MG-ADL items compared to the Day 1 MG-ADL score or new or worsening of respiratory/bulbar symptoms. Rescue therapy can include IVIg, plasma exchange, change in the SoC OCS dose, and use of new CS. If rescue therapy is needed, the Sponsor should be informed, preferably prior to the administration of treatment, where possible, without compromising the participant's safety (see [Section 6.8.3](#)). In case of use of rescue therapy during the DB period, the study intervention will be permanently discontinued.

If a participant prematurely and permanently discontinues treatment with the IMP during the DB period, the participant will be asked to perform a pEOT visit and to continue to perform DB period visits without IMP. If the participant is not willing to continue with DB study visits without IMP, there will be a safety FU period (4 to 8 weeks) after the pEOT.

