7.1 DISCONTINUATION OF STUDY INTERVENTION

7.1.1 Permanent discontinuation

Permanent intervention discontinuation is any treatment discontinuation associated with the definitive decision from the Investigator or the participant not to re-expose the participant to the study intervention at any time.

In rare instances, it may be necessary for a participant to permanently discontinue study intervention.

During the DB period, the use of rescue therapy will lead to permanent discontinuation of the study intervention.

The following may also be justifiable reasons for the Investigator or Sponsor to discontinue a participant from the study intervention:

- Adverse events that endanger the safety of the participant, or if discontinuation of study intervention is desired or considered necessary by the Investigator and/or participant.
- If IMP discontinuation criteria are met as per guidance for the FU of laboratory abnormalities in Appendix 6 ([Section 10.6](#)).
- At participant's request, ie, withdrawal of the consent for treatment.
- If a female participant becomes pregnant or wishes to become pregnant during the study.
- Any serious opportunistic infections.
- Continued need for/chronic use of a prohibited concomitant medication (see [Section 6.8](#), Appendix 10 [[Section 10.10](#)]).

Any abnormal laboratory value or ECG parameter will be immediately rechecked for confirmation after 24 hours before making a decision of permanent discontinuation of the IMP for the concerned participant.

Handling of participants after permanent intervention discontinuation

[figure not shown]
Participants will be followed up according to the study procedures specified in this protocol up to the scheduled date of study completion, or up to recovery or stabilization of any AE to be followed up as specified in this protocol, whichever comes last.

During the DB period, if possible, and after the definitive discontinuation of study intervention, the participants should be encouraged to come back as soon as possible for the pEOT visit and will be assessed using the procedures planned for the visit. Participants will be asked to continue in the study, attending all scheduled visits as per SoA ([Section 1.3](#)) if possible until the end of the DB period. If the participant does not agree to the full visit schedule per SoA after a decision for permanent end of treatment (EOT), the FU visit (4 to 8 weeks after pEOT) will be performed.

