9 STATISTICAL CONSIDERATIONS

The data from the placebo-controlled and the OLE treatment phases will be the focus of the clinical study report of the respective phase. The following statistical methods/considerations relate to the analysis of the data from the placebo-controlled period. The data from the open-label portion are non-controlled and supportive in nature; summary statistics will be provided for each of the efficacy variables and for safety data.

The null hypothesis for the primary efficacy endpoint of the change from baseline in MG-ADL score at Week 26 is that there is no treatment difference between tolebrutinib and placebo, and the alternative is that there is a between-treatment difference. To strongly control the type I error rate for the study, a procedure will be applied at a 2-sided 5% significance level. If tolebrutinib is significant for the primary endpoint, a selective set of secondary endpoints will be tested following a pre-specified procedure. The complete list of the secondary endpoints that will be adjusted for multiplicity will be detailed in the statistical analysis plan (SAP) prior to the interim database lock. The study will be declared positive at the final analysis if the null hypothesis for the change from baseline in MG-ADL score at Week 26 for tolebrutinib versus placebo is rejected.

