9.1 SAMPLE SIZE DETERMINATION

A total sample size of [REDACTED] participants (randomization ratio 1:1, ie, [REDACTED] [REDACTED]) is needed to have at least 80% power to demonstrate superiority of tolebrutinib versus placebo (0.05 2-sided significance level) based on the following assumptions on the primary endpoint (change from baseline in MG-ADL total score at Week 26):

- True mean difference of -2 between tolebrutinib and placebo.
- Common standard deviation (SD) of 4.
- 15% early discontinuation from the treatment/study.

Calculations were made using East[®] 6.5.

Randomization will be stratified by MGFA class (II, IIIa/IVa, or IIIb/IVb) and region (US, non-US).

[REDACTED]

[REDACTED]

[REDACTED]

[REDACTED]

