9.3.1 General considerations

The baseline value of efficacy parameters is defined as the last available value prior to the first dose of the study medication unless otherwise specified. The baseline value of safety parameters is defined as the last available value prior to the first dose of IMP. For participants randomized but not treated, the baseline value is defined as the last available value before randomization.

Unless otherwise specified, analyses will be performed by treatment group (and overall for baseline and demographic characteristics).

The observation period will be divided into 4 segments:

- The pre-treatment period is defined as the period from signed informed consent up to the first IMP administration.
- The on-treatment period (ie, TE period) for the DB period is defined as the period from the first IMP administration to the earliest of 1) last IMP administration plus 10 days, 2) first IMP in the OLE, 3) death date, or 4) last contact date.
- The on-treatment period for the OLE is defined as the first IMP administration in the OLE to the earliest of 1) last IMP administration plus 10 days, 2) death date, or 3) last contact date.
- If applicable, the post-treatment period is defined as the period from the end of the on-treatment period to the last contact date.

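### Double-blind AE tables give only crude percentages; if stopping differs between arms they compare unequal time at risk, so person-time rates and cumulative incidence should be added

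*Combined protocol and SAP*

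**What the plan says.** Section 9.3.5.1 defines the events that enter the main tables as "TEAEs: AEs that developed, worsened, or became serious during the DB on-treatment period". It plans incidence tables by arm for all TEAEs, AESIs, SAEs and AEs leading to permanent discontinuation, and gives the measure: "The AE summaries will be generated with number (%) of participants experiencing at least one event". Section 9.3.1 ends the double-blind on-treatment period at the earliest of "1) last IMP administration plus 10 days, 2) first IMP in the OLE, 3) death date, or 4) last contact date". Later events go to a separate post-treatment category.

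Section 7.1.1 states: "During the DB period, the use of rescue therapy will lead to permanent discontinuation of the study intervention". Section 4.1 sets the planned length: "The DB period will include a screening period (up to 28 days) and a treatment period of 26 weeks". The only assumption about stopping is in section 9.1: "15% early discontinuation from the treatment/study". It is not split by arm, cause or time.

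Section 9.3.5 makes safety descriptive, without tests. For the open-label extension, section 9 says only that "summary statistics will be provided for each of the efficacy variables and for safety data". The text reviewed has no person-time denominator, exposure-adjusted rate or time-to-event display for AEs.

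**The concern.** A crude percentage of participants with an event is comparable between arms only if the arms are observed for similar times. Here the observation window is tied to dosing, and dosing is tied to outcome. Section 2.3.2 lists less need for rescue among the hoped-for benefits. If that happens, more placebo participants stop, their windows close sooner, and the placebo percentages fall for a reason unrelated to AE risk. Section 2.3.1 also names drug-induced liver injury as an identified risk, and section 7.1.1 allows stops for laboratory findings. Those stops could shorten exposure on tolebrutinib and lower its percentages instead.

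The between-arm safety comparison is a secondary objective of the double-blind period. With no tests planned, readers will rely on the displayed numbers, and from n (%) alone they cannot tell whether a gap reflects risk or exposure.

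**Working it through.** **No plan figure to reproduce.** The document states no AE rate, exposure time or rescue rate, and the sample size is redacted. The figures below are scenarios.

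**Inputs from the plan.** Treatment period 26 weeks (section 4.1); window tail 10 days = 10/7 = 1.43 weeks (section 9.3.1); pooled stopping 15% (section 9.1).

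**Assumptions.** The same constant AE hazard in both arms; full-period risk R of 5% or 30%; stopping of 10% versus 20% at Week 13 (averaging 15%), or, as an extreme, 5% versus 25% at Week 8 (also averaging 15%).

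**Formulas.** Weekly hazard λ = −ln(1 − R)/26. A participant who stops at week t has risk q = 1 − exp(−λ(t + 1.43)). With a proportion p stopping, crude risk = (1 − p)R + pq.

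**30% AE.** λ = 0.01372.
- Stop at Week 13: q = 17.96%. With p = 10%, 0.90 × 30 + 0.10 × 17.96 = 28.8%. With p = 20%, 0.80 × 30 + 0.20 × 17.96 = 27.6%. Gap 1.2 points.
- Stop at Week 8: q = 12.13%. With p = 5%, 29.1%; with p = 25%, 25.5%. Gap 3.6 points.

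**5% AE.** λ = 0.001973.
- Stop at Week 13: q = 2.81%; 4.78% versus 4.56%. Gap 0.2 points.
- Stop at Week 8: q = 1.84%; 4.84% versus 4.21%. Gap 0.6 points.

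**Equal stopping.** With 15% in both arms at Week 13, the 30% AE shows 28.2% in each arm. Gap zero.

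**What a person-time rate does.** Under a constant hazard, expected time to first event or end of window equals crude risk divided by λ, so events divided by person-time returns λ in both arms: 71.6 per 100 participant-years for the 30% AE and 10.3 for the 5% AE, in every scenario.

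**Where the rate fails.** Put all the hazard in Weeks 0 to 12 with 30% risk, and let 5% versus 25% stop at Week 13. Crude risk is 30% in both arms, which is correct. The hazard is −ln(0.7)/12 = 0.02972 per week, so mean person-time in Weeks 0 to 12 is 0.30/0.02972 = 10.09 weeks. The event-free 70% then add 14 weeks if they continue and 2.43 weeks if they stop:
- p = 5%: 10.09 + 0.7 × (0.95 × 14 + 0.05 × 2.43) = 19.49 weeks; 0.30/19.49 × 5,218 = 80.3 per 100 participant-years.
- p = 25%: 10.09 + 0.7 × (0.75 × 14 + 0.25 × 2.43) = 17.87 weeks; rate 87.6.

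(5,218 is 100 × 365.25/7.) The rate alone shows a false excess of about 9%, while Week 26 cumulative incidence stays at 30% in both arms.

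**Extension.** If 20% to 50% leave evenly over 104 weeks (assumed) and the 2-year risk is 5% to 30%, the crude percentage is about 0.75 to 0.91 of that risk.

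**Scale against noise.** A difference of 2, SD 4, two-sided 0.05 and 80% power need about 63 per arm, and 63/0.85 is about 75. With that assumed size, the standard error of a difference is √(2 × 0.3 × 0.7/75) = 7.5 points at 30% risk and 3.6 points at 5%.

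**The case against.** Four objections carry weight.

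First, section 9.3 describes itself as a summary and leaves technical detail to a SAP, and no separate SAP text is in the material reviewed. A reader might infer that the sponsor decided against exposure adjustment. The documents do not show that; they show that n (%) is named and nothing else is.

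Second, the shift is small. SAEs and AESIs are more likely to sit near 5% than 30% (an assumption), where the gap is 0.2 to 0.6 points. Even the extreme case for a 30% AE, 3.6 points, is about half of one standard error at the assumed size. A reader might expect a false AE excess of several points for an effective drug. That needs a fivefold imbalance in early stopping, for which the plan gives no basis. Placebo rescue and tolebrutinib safety stops also pull in opposite directions. What survives is that the shift is systematic, so pooling studies with the same pattern would not remove it.

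Third, a reader might infer that harm would go unseen. An AE that causes a stop is counted before the stop and has its own table. AEs are collected to the final visit (section 8.3.1), and post-treatment AEs and deaths are analysed separately. The gap is in comparability, not in data capture.

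Fourth, the artefact does not carry over to the extension. That phase has one arm, rescue there does not force a stop (section 4.1), and the n (%) rule is written for the double-blind period. Only the narrower risk remains, that a percentage over variable follow-up is read as a 2-year risk.

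**Conclusion.** The point holds as a conditional one. The double-blind AE measure takes no account of time at risk, and the window and rescue rules make that time depend on outcome. If stopping differs between arms, the percentages differ even with identical hazards. Under equal constant hazards the distortion is about 1.2 points for a 30% AE and 0.2 for a 5% AE in the moderate scenario, about 3.6 and 0.6 in the extreme one, and nil with equal stopping. It can favour either arm. The stopping rates and times are assumptions, because the plan gives a single pooled figure. The documents do not establish that exposure will differ, that a safety signal would be masked, or that the extension has a between-arm bias. The addition is still worth making, because it is cheap and uses data already collected.

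**What to change.** In section 9.3.5.1, or in the SAP before unblinding, keep n (%) and add for the double-blind period:

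1. Total treatment-emergent participant-years per arm.
2. Participants with a first event per 100 participant-years, with time from first dose to the event or the end of the window, and a descriptive rate difference with 95% CI.
3. Cumulative incidence at Week 26 by arm, censoring at the end of the treatment-emergent window with death as a competing event. Stopping treatment should not itself be handled as a competing event, since that would return the crude percentage.

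Apply all three to all TEAEs, SAEs, AESIs and AEs leading to discontinuation. Limiting cumulative incidence to AESIs would leave the other categories exposed to the early-hazard problem shown above.

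For the extension, report participant-years and cumulative incidence over time.

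The cost is a paragraph of SAP wording and a few table columns. Dosing and AEs are already recorded (sections 6.4 and 8.3.1), and no visit, stopping rule or rescue rule changes. The rates assume a roughly constant hazard, and the cumulative incidence assumes that stopping is unrelated to later AE risk, so both belong beside n (%) and not in its place. If the SAP already plans these displays, one cross-reference closes the point.

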9.3.5.2 Laboratory variables, vital signs, and electrocardiograms (ECGs)

Quantitative analyses

For laboratory variables, vital signs, and ECG variables, descriptive statistics for results and changes from baseline will be provided for each analysis window during the on-treatment period. These analyses will be performed using central measurements only (when available) for laboratory variables and ECG variables.

Analyses according to PCSA

Potentially clinically significant abnormalities analyses will be performed based on the Sponsor's PCSA list currently in effect at the time of the database lock.

Analyses according to PCSA will be performed based on the worst value during the DB on-treatment period, using all measurements (either local or central, either scheduled, nonscheduled or repeated).

For laboratory variables, vital signs, and ECG variables, the incidence of participants with at least one PCSA during the TE period will be summarized regardless of the baseline level and according to the following baseline status categories:

- Normal/missing
- Abnormal according to PCSA criterion or criteria

[figure not shown]
For ECG, the incidence of participants with at least one abnormal ECG during the TE period will be summarized regardless of the baseline level and according to the following baseline status categories:

[figure not shown]
- Normal/missing
- Abnormal

9.3.6 Other analysis

For a regional or national emergency declared by a governmental agency, contingency measures are included in ([Section 10.9](#)) Appendix 9: Contingency measures for a regional or national emergency that is declared by a governmental agency.

10 SUPPORTING DOCUMENTATION AND OPERATIONAL CONSIDERATIONS

10.1 APPENDIX 1: REGULATORY, ETHICAL, AND STUDY OVERSIGHT CONSIDERATIONS

10.1.1 Regulatory and ethical considerations

- This study will be conducted in accordance with the protocol and with the following:
 - Consensus ethical principles derived from international guidelines including the Declaration of Helsinki and the applicable amendments and Council for International Organizations of Medical Sciences (CIOMS) International Ethical Guidelines
 - Applicable ICH-GCP Guidelines
 - Applicable laws and regulations (eg, data protection law as General Data Protection Regulation - [GDPR]).
- The protocol, protocol amendments, ICF, IB, and other relevant documents (eg, advertisements) must be submitted to an IRB/IEC by the Investigator and reviewed and approved by the IRB/IEC before the study is initiated.
- Any amendments to the protocol will require IRB/IEC approval before implementation of changes made to the study design, except for changes necessary to eliminate an immediate hazard to study participants.
- Protocols and any substantial amendments to the protocol will require health authority approval prior to initiation except for changes necessary to eliminate an immediate hazard to study participants.
- The Investigator will be responsible for the following:
 - Providing written summaries of the status of the study to the IRB/IEC annually or more frequently in accordance with the requirements, policies, and procedures established by the IRB/IEC
 - Determining whether an incidental finding (as per Sanofi policy) should be returned to a participant and, if it meets the appropriate criteria, to ensure the finding is returned (an incidental finding is a previously undiagnosed medical condition that is discovered unintentionally and is unrelated to the aims of the study for which the tests are being performed). The following should be considered when determining the return of an incidental finding:
 - The return of such information to the study participant (and/or his/her designated healthcare professional, if so designated by the participant) is consistent with all applicable national, state, or regional laws and regulations in the country where the study is being conducted, and
 - The finding reveals a substantial risk of a serious health condition or has reproductive importance, AND has analytical validity, AND has clinical validity.

- The participant in a clinical study has the right to opt out of being notified by the Investigator of such incidental findings. In the event that the participant has opted out of being notified and the finding has consequences for other individuals, eg, the finding relates to a communicable disease, Investigators should seek independent ethical advice before determining next steps.
- In case the participant has decided to opt out, the Investigator must record in the site medical files that she/he does not want to know about such findings.
- Notifying the IRB/IEC of SAEs or other significant safety findings as required by IRB/IEC procedures.
- Providing oversight of the conduct of the study at the site and adherence to requirements of 21 Code of Federal Regulations (CFR), ICH guidelines, the IRB/IEC, European regulation 536/2014 for clinical studies (if applicable), European Medical Device Regulation 2017/745 for clinical device research (if applicable), and all other applicable local regulations.

As applicable, according to Directive 2001/20/EC, the Sponsor will be responsible for obtaining approval from the Competent Authorities of the EU Member States and/or Ethics Committees, as appropriate, for any amendments to the clinical trial that are deemed as “substantial” (ie, changes which are likely to have a significant impact on the safety or physical or mental integrity of the clinical trial participants or on the scientific value of the trial) prior to their implementation.

